## **Statistical Analysis Plan**

Categorical data are presented as numbers with percentages, and tests for significant differences between the groups are assessed with  $\chi^2$  test. Continuous data are presented as mean (95% CI) or as median with inter-quartile range or range and assessed for normal distribution with the Kolmogorov-Smirnov/Shapiro-Wilk test. Tests for significant differences between groups are performed with an independent-samples t-test or Mann-Whitney U test when appropriate. The primary outcome is evaluated using  $\chi^2$  test, and the different modalities in the discharge criterion system and length of stay (secondary outcome) are evaluated using the independent-samples Mann-Whitney U test. Need for seroma drainage, readmissions and wound infections are evaluated using  $\chi^2$  test.

All available data are used, missing data is not imputed. Data from the questionnaire on PONV and sleep is dichotomized into categories, PONV/no PONV and sleep problems/no sleep problems. A two-sided 5% significance level is chosen for the primary and secondary outcomes. To adjust for multiple comparisons in the tertiary outcome (questionnaire, 40 tests), we chose a Bonferroni corrected significance level of 0.125%.

Data analyses were conducted using SPSS for Windows, version 22 (IBM Corp., New York, USA).

Data processing is done by the investigator, who will continue to be blinded until all results are analyzed, and the abstract is written and accepted by co-authors.

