### **Blinding**

Participants, all healthcare providers, trial personnel, data monitoring committee, principal investigator and outcome adjudicators will be blinded throughout the study. After trial completion, the principal investigator receives the allocation sequence without intervention revealed. The intervention allocation will be revealed after performing statistical analysis and drafting the paper, including comments from all authors.

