#### **Sample size**

After modification of our ERAS protocol introducing high-dose glucocorticoids (125 mg methylprednisolone (equivalent to 24 mg dexamethasone) we observed a 30 % to 10 % decrease in PACU referral after mastectomy. To test the isolated effect of the increased glucocorticoid dosage in a well-implemented ERAS protocol, we chose to compare 24 vs 8 mg dexamethasone. Considering the observed 20 % absolute (66% relative) reduction in need for PACU transfer clinically relevant, a sample size of 130 patients (65 in each group) was calculated ([www.sealedenvelope.com](http://www.sealedenvelope.com)) with a two-sided 5 % significance level, a power of 80 % and an anticipated 10 % exclusion rate.

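### Does the primary outcome need a pre-specified risk difference, confidence interval and rule for reading a non-significant result?

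*Combined protocol and SAP*

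**What the plan says.** **Analysis.** The Statistical Analysis Plan covers categorical outcomes in one sentence: "Categorical data are presented as numbers with percentages, and tests for significant differences between the groups are assessed with" a chi-square test. It then repeats the choice for the main result: "The primary outcome is evaluated using" a chi-square test, at a two-sided 5% level. The only confidence interval it mentions is for other data: "Continuous data are presented as mean (95% CI) or as median". On missing data it says: "All available data are used, missing data is not imputed".

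**Design and blinding.** The Study design section states superiority and gives no margin. Under Blinding, "After trial completion, the principal investigator receives the allocation sequence without intervention revealed", and the intervention is disclosed only after the analysis is done and the paper drafted. The Statistical Analysis Plan likewise has the abstract agreed while the investigator is still blinded.

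**Target effect.** The Sample size section reports that after a change of steroid regimen "we observed a 30 % to 10 % decrease in PACU referral after mastectomy". It sets the target with the words "Considering the observed 20 % absolute (66% relative) reduction in need for PACU transfer clinically relevant", and arrives at 130 patients with 80% power and a 10% allowance for exclusions.

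**Allocation.** Inclusion and preoperative treatment says that patients are randomised when they enrol. The Randomization section provides 130 numbered envelopes.

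**The concern.** A p-value does not measure an effect. If the chi-square test is non-significant, a reader needs to know whether a 20-point reduction has been ruled out. The plan provides an interval for means but none for the outcome on which the trial is sized. The effect scale, the interval method and the reading of a null result could then be chosen after the data are seen. The abstract is also settled on coded groups, which seems to call for a reading rule fixed in advance. What is at stake is that an inconclusive trial might be reported as showing no difference.

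Two further points appear to add weight.

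- **Regimens.** The 20-point target is an uncontrolled before-after change, and the Introduction admits that closer attention may explain part of it. The Introduction names 24 mg dexamethasone as the new regimen, while the Sample size section names 125 mg methylprednisolone. Neither gives the steroid regimen behind the 30%, although 30% serves as the rate for the 8 mg arm. The Introduction also says both that all mastectomy patients have had 24 mg since mid-2015 and that 8 mg is already given to all patients.
- **Exclusions.** The 130 envelopes equal a total that already contains the exclusion allowance, so exclusions seem to fall after allocation.

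**Working it through.** **1. The plan's own figure.** Inputs from the Sample size section: 30% versus 10%, two-sided 5%, 80% power, 10% exclusions.

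- n per arm = (1.960 + 0.842)² × [0.30×0.70 + 0.10×0.90] / 0.20² = 7.849 × 0.30 / 0.04 = 58.87, rounded up to 59.
- 59 × 1.10 = 64.9, rounded up to 65 per arm, or 130 in total. This matches the plan.
- Dividing by 0.9 instead gives 118 / 0.9 = 131.1, or 132 in equal arms, a difference of two patients.

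**2. How often the test is non-significant.** I enumerated all pairs of binomial counts and applied the Pearson chi-square test without continuity correction, at true rates of 30% and 10%.

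| Evaluable per arm | Power | Non-significant |
|---|---|---|
| 58/59 | 79.5% | 20.5% |
| 59/59 | 80.5% | 19.5% |
| 65/65 | 83.2% | 16.8% |

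**3. What the interval would show.** I used the Newcombe 95% interval for the risk difference (8 mg minus 24 mg). At 59/59 its mean width is 28 points. Among the non-significant trials, 85.3% have an upper limit of at least 20 points, so the share of all trials is 0.195 × 0.853 = 0.166, about 17%. With no true effect, the corresponding share of non-significant trials is 4% (both arms 10%), 20% (both 20%) or 30% (both 30%). These equal rates are assumed.

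**4. Can a reader recover the interval from what the plan presents?** Yes, because the four numbers suffice. With assumed counts:

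| Counts | p | Difference (points) | 95% CI |
|---|---|---|---|
| 12/59 vs 6/59 | 0.12 | 10.2 | -3.1 to 23.3 |
| 9/59 vs 6/59 | 0.41 | 5.1 | -7.4 to 17.6 |

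**5. Would the addition alter a decision?** No. The chi-square test would still decide significance. The interval can only introduce a borderline conflict: 14/59 vs 6/59 gives p = 0.0497 with an interval of -0.1 to 27.0. At 30% versus 10% such conflicts occur in 1.2% of trials at 59/59, 0.3% at 58/59 and 0.05% at 65/65.

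**6. Could a 20-point reading rule work on coded groups?** Not as a one-sided question. While the arms are labelled only A and B, the direction of benefit is unknown, so the interval would have to be checked against both +20 and -20 points. Blinded drafting therefore makes such a rule less simple than it sounds.

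**7. Exclusions after allocation.** The most that avoiding them could gain is 83.2% - 80.5% = 2.7 points of power, and that assumes no exclusions at all.

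**The case for a change.** The best case for a change is that it is almost free. It needs one estimate from data already collected and a few sentences, and in return about one trial in six is protected from a misleading null if the planned effect is real. The protocol also gives some reason for caution. Its Aim section expects no difference in wound infection, seroma and readmissions, these outcomes are also tested by chi-square, and the design has no margin. A statement that non-significance is not equivalence would be useful there too.

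This stands as reporting advice. It does not show that anything in the plan is wrong. The 17% follows from 80% power and is the same with or without a pre-stated interval. Leaving the scale open gives little room for selection, because the risk difference and risk ratio come from the same counts and neither decides significance.

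The regimen point is a fair criticism of the text. "To test the isolated effect of the increased glucocorticoid dosage" presupposes a known baseline, and none is given. The Introduction and the Sample size section must be reconciled on which regimens lie behind the two rates. The Sample size section calls the two drugs' doses equivalent, which softens the mismatch. If the true rates were 20% versus 10%, power at 59 per arm would be about 33% (pooled approximation, assumed rates). That is the usual risk of a target taken from before-after data, and the protocol discloses it. Reconciling the wording would not alter the analysis or the 130.

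On exclusions, the timing of randomisation is stated and nothing contradicts it. That exclusions follow allocation is an inference. Participants, providers and trial personnel are blinded and the syringes look identical, so there is no evident route to bias. Naming the reasons for exclusion and reporting them by arm is ordinary practice. Randomising later could cost logistics for at most 2.7 points of power.

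**Conclusion.** No change to the plan follows. The omission is real, but it is a detail that analysts ordinarily supply: a risk difference with its 95% interval beside the chi-square result, computed from counts the plan already presents. Followed exactly as written, the plan gives a sound superiority decision on an adequately calculated sample, and no stated number or rule is wrong.

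The size of the issue is bounded. About 17% of trials would be non-significant with an interval still reaching 20 points, given true rates of 30% and 10%, 59 evaluable patients per arm, an uncorrected Pearson test and Newcombe intervals. With no true effect, the share of non-significant trials in that position is 4% to 30%, depending on the common rate. The conclusion also rests on the documents nowhere stating that a non-significant primary result will be called no difference. If a report did so, the fault would lie in the reporting, and the published counts would expose it.

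The inconsistent account of the earlier regimens should be reconciled in the text, without effect on the analysis or sample size. The timing of randomisation needs no clarification.

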**Appendix 1. Danish Society of Anesthesiology and Intensive Care Medicine (DASAIM)- score, modified.**

## Introduction

Post-surgery, patients are traditionally observed and treated in post-anesthesia care units (PACU) until they are discharged to the ward (or directly home) assessed by standardized international discharge criteria.

The research project "Why in PACU?" (Rigshospitalet, Denmark), has since the beginning of 2016 systematically collected and analyzed procedure-related complications in the recovery phase. The complications include pain, nausea/vomiting, circulatory and respiratory problems, orthostatic intolerance and cognitive disorders. Common to all the above-mentioned post-operative problems are the possible links to the inflammatory response caused by the surgical trauma.

Glucocorticoids can in this context be central for the reduction of acute postoperative organ dysfunctions, caused by the anti-inflammatory effect. In a number of different surgical procedures, single dose, pre-operative glucocorticoids have been shown to reduce post-operative nausea and vomiting (PONV), acute pain and need of opioids as well as accelerate the convalescence.

Meta-analyses also showed that single-dose administration of glucocorticoids (methylprednisolone and dexamethasone) for surgical patients is safe as opposed to long-term treatment.

Based on positive results in other procedure-specific studies, all mastectomy patients at Rigshospitalet, have received pre-operative high-dose steroids, in the form of 24 mg dexamethasone injection since mid-2015. This has resulted in a decrease in the proportion of patients who need observation in PACU from 30 % to 10 %. The reduction is primarily due to less pain, less sedation, and lower opioid administration.

Whether this is also partly due to a "systemic effect" (Hawthorn effect) as a result of increased focus on the area cannot be excluded.

Prior to creating clinical recommendations and standards, it is required that the results be tested in a randomized, controlled, clinical trial.

The study is not placebo-controlled since the positive effects of dexamethasone 8 mg on PONV have been shown in numerous trials and is already being administered to all patients at the clinic. It would therefore not be ethically correct to withdraw from this practice.

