## **Aim**

The aim of this study is to investigate the effect of a single preoperative high-dose steroid injection on complications in the immediate postoperative phase after breast cancer surgery, with removal of the breast (mastectomy). Primary outcome is the proportion patients who require transfer to the post anesthesia care unit (PACU) and the proportion that can be transferred directly to the ward. Secondary outcomes are organ specific complications in the post anesthesia phase, pain and nausea the first 5 days, seroma and wound infection the first 14 days and readmissions the first 30 days after surgery.

The investigators hypothesize that the frequency of transfer to the PACU and organ specific complications will be lower among patients receiving high dose dexamethasone. The investigators hypothesize, that there will be no difference in wound infections, seroma or readmissions.

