## **Methods**

### **Study design**

Randomized, double-blind, controlled intervention study. Superiority design.

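### The Aim hypothesises no difference in wound infection, seroma and readmission, but the planned chi-square test can only refute that, and no estimate, interval or margin is planned

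*Combined protocol and SAP*

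**What the plan says.** The Aim states two kinds of hypothesis. PACU transfer and organ-specific complications are expected to be lower with the higher dose. For three other outcomes the wording is "The investigators hypothesize, that there will be no difference in wound infections, seroma or readmissions".

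The Statistical Analysis Plan gives both kinds the same tool. The general rule is "Categorical data are presented as numbers with percentages, and tests for significant differences between the groups are assessed with" a chi-square test. For the three outcomes it adds that "Need for seroma drainage, readmissions and wound infections are evaluated using" the same test. Primary and secondary outcomes are tested at a two-sided 5% level. The only confidence interval mentioned is for means of continuous data.

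Study design describes the trial as "Randomized, double-blind, controlled intervention study. Superiority design". Under Sample size, the calculation rests on PACU transfer alone: the sponsor considered the observed 20-point "reduction in need for PACU transfer clinically relevant, a sample size of 130 patients (65 in each group) was calculated". No equivalence or non-inferiority margin appears in the documents.

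**The concern.** A test of difference has two outcomes: it rejects equality, or it fails to. Failing to reject is not evidence for equality unless the data also exclude differences that matter, and that takes an interval read against a stated margin or, at the least, an honest statement of what has not been excluded. The plan has neither.

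The primary outcome has no planned interval either, but its hypothesis is a difference, which the test can support. The mismatch between hypothesis and method is specific to wound infection, seroma and readmission.

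These are the outcomes for which the Aim expects no harm from the higher dose. The Introduction sets the purpose: "Prior to creating clinical recommendations and standards, it is required that the results be tested in a randomized, controlled, clinical trial". If p exceeds 0.05, the result will match the Aim's wording and can be taken as confirming it, even where the observed risk at 24 mg is well above that at 8 mg. The plan does not say it will be read that way, but it does nothing to prevent it.

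**Working it through.** **The plan's own sample size.** Inputs from Sample size: 30% v 10%, two-sided 5%, 80% power, 10% exclusions.

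n per arm = (1.960 + 0.842)² × (0.3×0.7 + 0.1×0.9) / 0.2² = 58.87, so 59 per arm and 118 in total. 118 × 1.10 = 129.8, which gives the stated 130. The figure reproduces, and it contains nothing about the three safety outcomes.

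**Inputs for the check.** Per-arm number: 65 × 0.9 = 58.5, taken as 58; results for all 65 are also given. The documents give no event rates, so counts of 0, 1, 3, 6, 12 and 17 events at 8 mg are *assumed* (0% to 29% of 58).

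**Method.** The chi-square test is uncorrected. The interval is Newcombe's: with d = p₁ − p₂ and Wilson limits (l₁, u₁) and (l₂, u₂),

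- lower limit = d − √[(p₁ − l₁)² + (u₂ − p₂)²]
- upper limit = d + √[(u₁ − p₁)² + (p₂ − l₂)²]

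**Worked example, 9/58 at 24 mg v 3/58 at 8 mg.**

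- χ² = 116 × (9×55 − 3×49)² / (58 × 58 × 12 × 104) = 3.35, p = 0.067. Fisher's exact p = 0.125. The smallest expected count is 6.
- d = 0.1552 − 0.0517 = 0.1034. Wilson limits: 0.0838 to 0.2693, and 0.0177 to 0.1414.
- Lower limit = 0.1034 − √(0.0714² + 0.0897²) = −0.011. Upper limit = 0.1034 + √(0.1142² + 0.0340²) = +0.223.

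So a threefold observed risk is non-significant, with an interval of −1.1 to +22.3 points.

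**Range, 58 per arm.** The third column is the largest 24 mg count that still gives p > 0.05.

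| Events at 8 mg | 95% CI if counts are equal (points) | Largest non-significant count at 24 mg | p | Observed excess (points) | Upper 95% limit (points) |
|---|---|---|---|---|---|
| 0 | ±6.2 | 3 | 0.079 | 5.2 | 14.1 |
| 1 | ±7.6 | 6 | 0.051 | 8.6 | 19.2 |
| 3 | ±9.6 | 9 | 0.067 | 10.3 | 22.3 |
| 6 | ±11.8 | 13 | 0.079 | 12.1 | 25.5 |
| 12 | ±14.7 | 21 | 0.064 | 15.5 | 30.9 |
| 17 | ±16.2 | 27 | 0.056 | 17.2 | 33.4 |

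With 0 v 0 events the chi-square statistic is undefined, while the interval still exists.

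**All 65 per arm retained.** Equal counts give ±5.6, 6.8, 8.6, 10.7, 13.4 and 14.9 points. The largest non-significant counts are 3, 6, 9, 14, 21 and 27, with upper limits of 12.7, 17.3, 20.1, 24.8, 28.1 and 30.6 points. The conclusion does not depend on the 10% allowance.

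**Power to detect harm, 65 per arm.** Exact power of the test against a true doubling of risk is 8% (2% to 4%), 19% (5% to 10%) and 35% (10% to 20%). At low base rates, a non-significant result is the likely one even if the risk doubles.

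**The case against.** The strongest reply is that nothing in the documents claims equivalence. To hypothesise no difference may be no more than an expectation, or the null that a two-sided test examines, and the design is openly labelled superiority. The plan does not say that p above 0.05 will be reported as no difference. Counts and percentages are reported, so any reader can compute an interval. The missing interval also applies to every categorical outcome.

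Much of this is right on the facts. No data are lost, and the harm needs a reading that the plan permits but does not prescribe. Even so, the Aim uses the same verb for these outcomes as for efficacy and the SAP gives them a formal test, so a reader will take the test as the answer to the hypothesis. It cannot be that answer when it is non-significant.

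Three narrower points stand. The tabulated excesses are deliberately the largest that stay non-significant; results of that kind are inconclusive and do not demonstrate harm. The two lowest-count thresholds (3 v 0 and 6 v 1) have smallest expected counts of 1.5 and 3.5, where an uncorrected chi-square is unreliable; the logic does not rest on them. And because the SAP and the Blinding section have results analysed and the paper drafted before the intervention is revealed, a conclusion about excess risk at 24 mg cannot be finished until afterwards.

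It could also be said that, once the SAP has a reading rule, the Aim can stay as an expectation. But without a margin the interval still could not confirm the hypothesis, so the Aim would keep a statement that the trial cannot support.

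**Conclusion.** The concern holds. The planned analysis can refute the hypothesis of no difference in wound infection, seroma or readmission, but no result of it can support that hypothesis. Under the assumed counts with 58 per arm, even identical observed risks leave differences of about 6 to 16 points unexcluded, and observed excesses of about 5 to 17 points at 24 mg would remain non-significant.

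These sizes rest on assumed event counts and an uncorrected test. The documents give no margin, so whether such intervals are acceptable is a clinical judgement. The logical point needs none of these assumptions. The primary analysis and the 130 patients are not affected. This should be changed, but it does not threaten the trial's main result.

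**What to change.** In the Statistical Analysis Plan, keep the chi-square test and add wording such as:

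> For wound infection, readmission and seroma requiring drainage, the main result is the risk difference (24 mg minus 8 mg) with a two-sided Newcombe 95% confidence interval. A p-value above 0.05 will not be reported as no difference; conclusions will state the largest excess risk that the interval does not exclude.

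Blinding is preserved. Under the Blinding section "the principal investigator receives the allocation sequence without intervention revealed", so report group A minus group B with both limits, and attach the direction once the groups are identified.

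In the Aim, replace the sentence hypothesising no difference with:

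> The differences between groups in the risks of wound infection, seroma requiring drainage and readmission will be estimated; no equivalence hypothesis is tested.

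Both edits are needed, because without a pre-specified margin an interval does not confirm no difference.

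The cost is wording: no new data or patients, and no change to the primary analysis. The interval needs only the four cell counts and can be calculated by hand if the named software does not offer it. Two costs should be accepted openly. The safety sentence in the draft must be completed after unblinding. And the conclusion becomes less favourable: an excess of up to about 8 points not excluded with 1 v 1 events, or about 16 points with 17 v 17.

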### **Secondary outcomes**

- Discharge score in the operating room (according to discharge criteria, Appendix 1).
- Discharge score at arrival to the ward or PACU (according to discharge criteria, Appendix 1).
- Complications/adverse events in the ward the first 24 h or until discharge.
- Length of stay (PACU/Hospital)
- Pain, self-reported in patient questionnaire. Days 0-4.
- Nausea/vomiting, self-reported in patient questionnaire. Days 0-4.
- Analgetics and antiemetics, use of, self-reported in patient questionnaire. Days 0-4.
- Quality of sleep, self-reported in patient questionnaire. Days 0-4.
- Feelings of anxiety, restlessness, fatigue, self-reported in patient questionnaire. Days 0-4.
- Seroma, requiring drainage, the first 14 postoperative days

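### The 40 questionnaire tests are not listed and are corrected by plain Bonferroni; listing them and using Holm keeps the same error control and never rejects fewer

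*Combined protocol and SAP*

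**What the plan says.** The Statistical Analysis Plan sets two significance rules. For the main outcomes: "A two-sided 5% significance level is chosen for the primary and secondary outcomes". For the questionnaire: "To adjust for multiple comparisons in the tertiary outcome (questionnaire, 40 tests), we chose a Bonferroni corrected significance level of 0.125" per cent. It does not list the 40 tests. On coding it says: "Data from the questionnaire on PONV and sleep is dichotomized into categories, PONV/no PONV and sleep problems/no sleep problems".

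The protocol has no tertiary tier. Its Aim section states: "Secondary outcomes are organ specific complications in the post anesthesia phase, pain and nausea the first 5 days". Its Secondary outcomes section lists every questionnaire outcome, among them "Pain, self-reported in patient questionnaire. Days 0-4", "Analgetics and antiemetics, use of, self-reported in patient questionnaire. Days 0-4" and "Feelings of anxiety, restlessness, fatigue, self-reported in patient questionnaire. Days 0-4".

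The section on clinical evaluations and outcome registration describes the questionnaire itself, with different contents. Pain is rated both on average and at worst, sadness stands where the outcome list has anxiety, and analgesic use appears without antiemetic use.

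On access to the allocation, the Blinding section says: "After trial completion, the principal investigator receives the allocation sequence without intervention revealed".

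**The concern.** There are three linked points.

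1. **Method.** A fixed 0.125% for every test is more conservative than family-wise control at 5% requires. Holm starts at the same 0.05/40 and relaxes the threshold after each rejection.
2. **Family.** The count of 40 fits two different sets of tests, so the SAP does not say which hypotheses are tested. Under the Blinding section the principal investigator holds the grouping before the arms are named. Two-sided p-values need only the grouping, so a family settled after that point could be chosen with the p-values known.
3. **Label.** The protocol's secondary tier and the SAP's tertiary tier conflict, and the SAP tests secondary outcomes at 5%.

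At stake is the evidence on pain and nausea over the first five days, which the Aim section names as secondary outcomes.

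**Working it through.** **The plan's own figure.** 0.05/40 = 0.00125 = 0.125%. It reproduces exactly.

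**What the 40 could be.** Days 0 to 4 are five days. With PONV as one binary item, as the SAP codes it:

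| Source | Items | Tests |
|---|---|---|
| Secondary outcomes | pain, PONV, analgesics, antiemetics, sleep, anxiety, restlessness, fatigue | 8 × 5 = 40 |
| Clinical evaluations and outcome registration | average pain, worst pain, PONV, analgesics, sleep, sadness, restlessness, fatigue | 8 × 5 = 40 |

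Six items are common (6 × 5 = 30 tests). Two differ (2 × 5 = 10 tests): antiemetics and anxiety in the first list, a second pain measure and sadness in the second. The first list does not say whether its pain item is average or worst.

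Other readings change the count. Splitting nausea from vomiting in the first list gives 9 × 5 = 45. Taking average nausea, worst nausea and vomiting separately in the second gives 10 × 5 = 50. With 50 tests, a 0.125% threshold bounds the family-wise error at 50 × 0.00125 = 6.25%, not 5%.

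**If the label were taken literally.** Forty tests at 5% would give 40 × 0.05 = 2 expected false positives under the null, and a family-wise error of 1 − 0.95^40 = 87% if independent. At 0.125% the latter is 1 − 0.99875^40 = 4.9%.

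**Power per test at 0.125%.** The documents give no effect sizes for the questionnaire, so these are assumptions: 59 per arm (65 × 0.9 = 58.5, rounded up), 0.5 SD for pain, and a range for binary items.

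- Pain, t-test: noncentrality 0.5 × √(59/2) = 2.716, 116 degrees of freedom, critical value 3.308; power 28.4%.
- Binary item, χ² test by exact binomial enumeration: 50% vs 30%, 14.8%; 40% vs 20%, 19.0%; 30% vs 10%, 29.2%.

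**Bonferroni against Holm.** Holm compares the k-th smallest of m p-values with 0.05/(m − k + 1) and stops at the first non-rejection. With m = 40 the limits are 0.00125 (k = 1), 0.00128 (k = 2), 0.00161 (k = 10), 0.0025 (k = 21) and 0.05 (k = 40). None is below 0.00125, so Holm cannot reject fewer tests.

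The size of the gain was simulated with 10,000 trials per case. Pain was tested by t-test and binary items by χ² (null rate 50%; 50% vs 30% if affected). Items were independent, with between-day correlation 0.5 on the latent scale. An affected item differs on all five days. Mean power per affected test, Bonferroni → Holm:

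| Affected items | Questionnaire description (2 pain, 6 binary) | Outcome list (1 pain, 7 binary) | Trials with at least one extra rejection |
|---|---|---|---|
| 1 | 28.2% → 28.6% | 28.0% → 28.4% | 2.0%; 2.0% |
| 2 | 28.0% → 28.8% | 21.3% → 22.0% | 7.9%; 6.0% |
| 4 | 21.3% → 22.6% | 18.2% → 19.4% | 20.3%; 18.8% |
| 8 | 18.1% → 20.6% | 16.4% → 18.7% | 52.8%; 49.1% |

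The last column gives the questionnaire description first, then the outcome list. At correlation 0.7 the results are close; the largest gain is 18.3% → 20.9%. Holm rejected fewer tests in none of the 200,000 simulated trials (2 families × 2 correlations × 5 cases, including no effect). Its family-wise error was 3.9% to 4.5% with no effect and 3.7% to 4.4% with one affected item.

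Stronger effects widen the gap. In a separate simulation of 40 independent z-tests with an assumed shift of 3.5, mean power rose from 60.7% to 61.4% with 5 true effects and from 60.8% to 75.3% with all 40.

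**The case against.** Bonferroni is valid and correctly computed here, so Holm is an efficiency gain and not the repair of an error. The gain is small and leaves every test underpowered under the assumed effects. The largest figures need all eight items to differ on all five days, and the Aim section states no hypothesis for sleep, mood or fatigue. All of this stands.

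Holm is also more sensitive to an unsettled family. With a fixed 0.125%, decisions on the 30 common tests do not depend on which list is used. Under Holm, a common test with p = 0.00127 is rejected (limit 0.05/39 = 0.00128) if a disputed test has p ≤ 0.00125. It is not rejected if that disputed test is left out and no other test reaches its limit. This is correct, and it is why the list must be fixed first; once it is, the objection falls away.

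The two families are inferred. One could read the outcome list as a summary and the questionnaire description, with the SAP's coding, as the real source of the 40. That is plausible, but antiemetic use and anxiety versus sadness still conflict. Choosing between items after seeing the coded groups is possible only where the patient form collected both versions, and the form is not in the documents. Average and worst pain, however, are both described as collected.

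Finally, the SAP attaches 0.125% to the questionnaire by name, so an analyst who follows it has one threshold. The tier conflict is a matter of labelling.

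**Conclusion.** The concern holds. Plain Bonferroni is valid, but Holm gives the same family-wise control and never rejects fewer tests. Under the stated assumptions it adds 0.4 to 2.6 percentage points of power per affected test, with at least one extra rejection in about 2% of trials (one affected item) to 49–54% (all eight). The direction of the gain is certain; its size depends on the assumed effects, 59 per arm, between-day correlation of 0.5 to 0.7 and independent items.

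The undefined family is the point to settle first: 10 of the 40 tests depend on which section the analyst follows. That both lists reach 40 is an inference that needs PONV as one item. The secondary/tertiary conflict is a label problem and does not by itself change the threshold. The primary outcome and the sample size are not affected.

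**What to change.** Make these changes before the principal investigator receives the coded allocation sequence:

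1. Reconcile the items in Secondary outcomes with those in the section on clinical evaluations and outcome registration: antiemetic use, anxiety or sadness, and average and/or worst pain. List the tests by item and day in the SAP, and set m to that count.
2. Replace the SAP's Bonferroni sentence with: *The m questionnaire tests are adjusted by Holm's method at a two-sided family-wise 5% level: p-values are sorted, the smallest is compared with 0.05/m, the next with 0.05/(m − 1), and so on, stopping at the first non-rejection.*
3. Use one tier name for the questionnaire in the SAP, the Aim and the Secondary outcomes sections, and state that the corrected rule applies to it, not the 5% rule.

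The cost is one sentence, a short table and some wording. Holm needs only the sorted p-values: no new data, software or patients. Its usual drawback, the loss of simple matching simultaneous intervals, does not arise because the SAP reports ordinary 95% intervals.
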